5.8 Criteria for Taking a Participant Off Study

Participants will be removed from study when any of the following criteria apply:

- Lost to follow-up
- Withdrawal of consent for data submission
- Death

The reason for taking a participant off study, and the date the participant was removed, must be documented in the case report form (CRF).

For Centralized Subject Registrations, the research team submits a completed Off Treatment/Off Study form to ODQ when a participant comes off study. This form can be found on the ODQ website or obtained from the ODQ registration staff. Other investigative sites will inform the Project Manager as soon as a participant is taken off study. The Project Manager will then make the relevant updates in OnCore.

For Decentralized Subject Registrations, the research team updates the relevant Off Treatment/Off Study information in OnCore.

6. DOSING DELAYS/DOSE MODIFICATIONS

Investigators should assess toxicities and make a determination which agent(s) is responsible for the toxicity and grade the toxicity. Dose delays and modifications will be made as indicated in the following table(s). The descriptions and grading scales found in the revised NCI Common Terminology Criteria for Adverse Events (CTCAE) version 4.0 will be utilized for dose delays and dose modifications. A copy of the CTCAE version 4.0 can be downloaded from the CTEP website

http://ctep.cancer.gov/protocolDevelopment/electronic_applications/ctc.htm.

6.1 Dose modifications for Pegylated Liposomal Doxorubicin

If patients experience treatment-related toxicities, their PLD dose should be reduced according to institutional prescribing and dose-reduction standards per the below tables.

If greater than two dose reductions are required, discussion and approval must be obtained by the Overall PI.

Recommended dose reductions for PLD (Doxil) per the FDA package insert:

Hand Foot Syndrome	
Toxicity	Dose Adjustment
Hand Foot Syndrome	
Grade 1: Mild erythema, swelling, or desquamation not interfering with daily activities	
• If no previous Grade 3 or 4 HFS, no dose adjustment.• If previous Grade 3 or 4 HFS, delay dose up to 2 weeks, then decrease dose by 25%.
Grade 2: Erythema, swelling, or desquamation interfering with, but not precluding normal physical activities; small blisters or ulcerations less than 2 cm. in diameter.	
• Delay dosing up to 2 weeks or until resolved to grade 0 or 1.• Discontinue doxil if no resolution after 2 weeks.• If resolved to grade 0 or 1 within 2 weeks: and no previous grade 3 or 4 HFS, continue treatment at previous dose or And previous Grade 3 or 4 toxicity; decrease dose by 25%
Grade 3: Blistering, ulceration, or swelling interfering	
• Delay dosing up to 2 weeks or until resolved to grade 0 or 1,

with walking or normal daily activities; cannot wear regular clothing.	
 then decrease dose by 25% • Discontinue doxil if no resolution after 2 weeks
Grade 4: Diffuse or local process causing infectious complications, or a bed ridden state or hospitalization.	
 • Delay dosing up to 2 weeks or until resolved to grade 0 or 1, then decrease dose by 25% • Discontinue doxil if no resolution after 2 weeks

Stomatitis

Toxicity	Dose Adjustment
Stomatitis	
Grade 1: Painless ulcers, erythema, or mild soreness	
 • If no previous Grade 3 or 4 toxicity, no dose adjustment. • If previous Grade 3 or 4 toxicity, delay dose up to 2 weeks, then decrease dose by 25%.
Grade 2: Painful erythema, edema or ulcers but can eat.	
 • Delay dosing up to 2 weeks or until resolved to grade 0 or 1. • Discontinue doxil if no resolution after 2 weeks. • If resolved to grade 0 or 1 within 2 weeks: 
and no previous grade 3 or 4 HFS, continue treatment at previous dose
 
or
 
And previous Grade 3 or 4 toxicity; decrease dose by 25%

Grade 3: Painful erythema, edema or ulcers and cannot eat.	
 • Delay dosing up to 2 weeks or until resolved to grade 0 or 1. Decrease dose by 25% and return to original dose interval • Discontinue doxil if no resolution after 2 weeks
Grade 4: Diffuse or local process causing infectious complications, or a bed ridden state or	
 • Delay dosing up to 2 weeks or until resolved to grade 0 or 1, then decrease dose by 25% and

hospitalization.	
 return to original dose interval • Discontinue doxil if no resolution after 2 weeks
------------------	--

Neutropenia and Thrombocytopenia

Toxicity	Dose Adjustment
Neutropenia and Thrombocytopenia	
Grade 1	No dose reduction
Grade 2	Delay until ANC \geq 1500 and plts \geq 100,000; resume treatment at previous dose
Grade 3	Delay until ANC \geq 1500 and plts \geq 100,000; resume treatment at previous dose
Grade 4	Delay until ANC \geq 1500 and plts \geq 100,000; resume at 25% dose reduction or continue previous dose with prophylactic granulocyte growth factor.

6.2 Dose Modifications for Pembrolizumab:

Adverse events (both non-serious and serious) associated with pembrolizumab exposure may represent an immunologic etiology. These adverse events may occur shortly after the first dose or several months after the last dose of treatment. Pembrolizumab must be withheld for drug-related toxicities and severe or life-threatening AEs as per Table 3 below. See Section 6.3.1 and Events of Clinical Interest Guidance Document for supportive care guidelines (**Appendix B**), including use of corticosteroids.

Table 3

Dose Modification Guidelines for Drug-Related Adverse Events (Please also see Appendix B)

Toxicity	Hold Treatment For Grade	Timing for Restarting Treatment	Discontinue Participant
Diarrhea/Colitis	2-3	Toxicity resolves to Grade 0-1.	Toxicity does not resolve within 12 weeks of last dose or inability to reduce corticosteroid to 10 mg or less of prednisone or equivalent per day within 12 weeks.
	4	Permanently discontinue	Permanently discontinue
AST, ALT, or Increased Bilirubin	2	Toxicity resolves to Grade 0-1	Toxicity does not resolve within 12 weeks of last dose.
	3-4	Permanently discontinue (see exception below) ¹	Permanently discontinue
Type 1 diabetes mellitus (if new onset) or	T1DM or 3-4	Hold pembrolizumab for new onset Type 1 diabetes mellitus or Grade 3-4 hyperglycemia associated	Resume pembrolizumab when patients are clinically and metabolically stable.

Toxicity	Hold Treatment For Grade	Timing for Restarting Treatment	Discontinue Participant
Hyperglycemia		with evidence of beta cell failure.	
Hypophysitis	2-3	Toxicity resolves to Grade 0-1	Toxicity does not resolve within 12 weeks of last dose or inability to reduce corticosteroid to 10 mg or less of prednisone or equivalent per day within 12 weeks.
	4	Permanently discontinue	Permanently discontinue
Hyperthyroidism	3	Toxicity resolves to Grade 0-1	Toxicity does not resolve within 12 weeks of last dose or inability to reduce corticosteroid to 10 mg or less of prednisone or equivalent per day within 12 weeks.
	4	Permanently discontinue	Permanently discontinue
Hypothyroidism	2-4	Therapy with pembrolizumab can be continued while treatment for the thyroid disorder is instituted	Therapy with pembrolizumab can be continued while treatment for the thyroid disorder is instituted.
Infusion Reaction	3-4	Permanently discontinue	Permanently discontinue
Pneumonitis	2	Toxicity resolves to Grade 0-1	Toxicity does not resolve within 12 weeks of last dose or inability to reduce corticosteroid to 10 mg or less of prednisone or equivalent per day within 12 weeks.
	3-4	Permanently discontinue	Permanently discontinue
Renal Failure or Nephritis	2	Toxicity resolves to Grade 0-1	Toxicity does not resolve within 12 weeks of last dose or inability to reduce corticosteroid to 10 mg or less of prednisone or equivalent per day within 12 weeks.
	3-4	Permanently discontinue	Permanently discontinue
All Other Drug-Related Toxicity ²	3 or Severe	Toxicity resolves to Grade 0-1	Toxicity does not resolve within 12 weeks of last dose or inability to reduce corticosteroid to 10 mg or less of prednisone or equivalent per day within 12 weeks.
	4	Permanently discontinue	Permanently discontinue

Note: Permanently discontinue for any severe or Grade 3 drug-related AE that recurs or any life-threatening event.

¹ For patients with liver metastasis who begin treatment with Grade 2 AST or ALT, if AST or ALT increases by greater than or equal to 50% relative to baseline and lasts for at least 1 week then patients should be discontinued.

² Patients with intolerable or persistent Grade 2 drug-related AE may hold study medication at physician discretion. Permanently discontinue study drug for persistent Grade 2 adverse reactions for which treatment with study drug has been held, that do not recover to Grade 0-1 within 12 weeks of the last dose.

After discussion and approval from the Overall PI, dosing interruptions are permitted in the case

of medical / surgical events or logistical reasons not related to study therapy (e.g., elective surgery, unrelated medical events, patient vacation, and/or holidays). The reason for interruption should be documented in the patient's study record.

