2.2 Pegylated Liposomal Doxorubicin (PLD)

PLD is approved in the U.S., Canada, and Europe for use in ovarian cancer following progression of cancer after platinum-based chemotherapy and represents a standard of care treatment for women with relapsed ovarian cancer (15).

PLD has demonstrated anti-cancer activity in both phase II and III studies; phase III studies have compared PLD to topotecan as well as other agents. Response rates for platinum resistant recurrent ovarian cancer are approximately 10%. Progression-free survival (PFS) for PLD in patients with recurrent ovarian cancer is approximately 3-4 months (12-14). Known toxicities of PLD include: hand-foot syndrome, mucositis, cardiotoxicity, myelosuppression, liver impairment, and infusion-related reactions. See the PLD Package Insert for other reported toxicities and additional details of clinical studies as well as toxicity management.

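### The grade 2 stomatitis row of the PLD dose table gives two conflicting instructions for a patient with earlier severe stomatitis but no severe hand-foot syndrome (minor)

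*Combined protocol and SAP*

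**What the plan says.** All of this is in section 6.1 (Dose modifications for Pegylated Liposomal Doxorubicin) unless stated otherwise.

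- **Stomatitis, grade 2, resolved to grade 0-1 within two weeks.** One branch reads "no previous grade 3 or 4 HFS, continue treatment at previous dose". The alternative reads "previous Grade 3 or 4 toxicity; decrease dose by 25" percent.
- **Stomatitis, grade 1.** The row uses *toxicity* in both branches: "If no previous Grade 3 or 4 toxicity, no dose adjustment", and "If previous Grade 3 or 4 toxicity, delay dose up to 2 weeks, then decrease dose by 25" percent.
- **Stomatitis, grade 3.** After a delay for recovery: "Decrease dose by 25% and return to original dose interval". The grade 4 row also cuts by 25%. A patient who continues PLD after a severe episode has therefore normally had one reduction already.
- **HFS, grade 2.** The same-dose branch carries the same HFS condition, which fits there because HFS is the toxicity being graded.
- **Status of the tables.** Section 6 says that delays and modifications follow the tables. Section 6.1 refers to "institutional prescribing and dose-reduction standards per the below tables" and heads the tables "Recommended dose reductions for PLD (Doxil) per the FDA package insert". Section 2.2 also sends the reader outside the protocol: "See the PLD Package Insert for other reported toxicities and additional details of clinical studies as well as toxicity management".

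Nothing in the protocol says which branch of the grade 2 stomatitis row takes priority.

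**The concern.** The two branches of a dosing rule should be mutually exclusive and should together cover every patient who reaches the row. Here one branch depends on earlier HFS and the other on earlier toxicity in a table about stomatitis, so the two conditions are not complements.

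At stake is the PLD dose after a recurrence in a patient who has already had severe stomatitis. Section 7.1.1 lists stomatitis among the most common PLD reactions. Approval from the Overall PI is required only beyond two reductions. The question here is whether a second reduction applies, so that safeguard would not catch the problem. A site could also not tell which of the two doses complies with the protocol.

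**Working it through.** The plan states no figure for this row, so there is none to reproduce. The check has two parts: which branch each history meets, and how far apart the resulting doses are.

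**1. Branch logic.** Take a patient whose grade 2 stomatitis has resolved within two weeks. The same-dose branch applies if there was no earlier grade 3-4 HFS. The cut applies if there was earlier grade 3-4 toxicity, and that word can be read in three ways.

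| Earlier grade 3-4 stomatitis | Earlier grade 3-4 HFS | *Toxicity* = stomatitis | *Toxicity* = stomatitis or HFS | *Toxicity* = HFS only |
|---|---|---|---|---|
| No | No | Same dose | Same dose | Same dose |
| **Yes** | **No** | **Both** | **Both** | Same dose |
| No | Yes | Neither | Cut 25% | Cut 25% |
| Yes | Yes | Cut 25% | Cut 25% | Cut 25% |

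The second line is the conflict. It disappears only if *toxicity* means HFS, but the Toxicity column of this table names stomatitis alone. Applied to the grade 1 row as well, that reading would make the table ignore earlier severe stomatitis. The third line shows a matching gap: if *toxicity* means stomatitis, a patient with earlier severe HFS only meets neither branch.

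**2. Size of the dose difference.** Inputs: starting dose 40 mg/m² (section 5.3.1.2), each reduction 25% (section 6.1). The text does not say whether a second 25% is taken from the current dose; I assume that it is.

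- After the earlier grade 3-4 stomatitis: 40 × 0.75 = 30 mg/m².
- Later grade 2 episode, same-dose branch: 30 mg/m².
- Later grade 2 episode, reduction branch: 30 × 0.75 = 22.5 mg/m². Gap: 30 − 22.5 = 7.5 mg/m².
- Later grade 1 episode in the same patient: 30 × 0.75 = 22.5 mg/m².
- Same-dose branch after grade 2 relative to the grade 1 outcome: 30 / 22.5 = 1.33, so the worse recurrence would be on a 33% higher dose.

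If each cut were instead 25% of the starting dose (10 mg/m²), the second step would be 30 − 10 = 20 mg/m² and the gap 10 mg/m².

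If the lead-in lowers the cohort dose to 30 mg/m² (section 5.1), the earlier episode gives 30 × 0.75 = 22.5. The branches then give 22.5 or 22.5 × 0.75 = 16.9 mg/m², a gap of 5.6.

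**3. How often.** The documents give no frequency for this sequence of events. Purely as an assumption, 1% to 5% of the 26 patients would be 26 × 0.01 = 0.3 to 26 × 0.05 = 1.3 patients.

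**4. Endpoints.** The DLT window is cycle 1 (section 5.4), and PLD is given once per 28-day cycle, so a PLD reduction can act from cycle 2 at the earliest. The rule of at least 10 of 26 patients with clinical benefit (section 13.4) does not depend on this wording.

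**The case against.** The best case against raising this is that it is a copying slip whose meaning can be recovered. The row directly above uses *toxicity* in both branches and reduces the dose after an earlier severe episode. No clinician would be expected to cut for a grade 1 recurrence and hold the dose for a grade 2 one. The tables are also not the only reference: they are presented as package-insert recommendations, to be used with institutional standards, and section 2.2 names the insert for toxicity management. The patient has normally had one reduction already, and stomatitis that stays unresolved after two weeks stops PLD in any case. The assumed patient counts are not evidence, and the 30 mg/m² cohort figures need two DLTs in the lead-in.

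Most of this stands, and it limits the weight of the point. Most readers would infer the reduction, and the number of patients affected is unknown and probably small. But none of it makes the printed row consistent. Section 6 makes these tables the operative instruction, and citing the insert does not tell a site that this row departs from what was intended. The insert was not available for this review, so it cannot be used to settle the wording either way.

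**Conclusion.** The row is wrong as written, and the error is minor. A patient with earlier grade 3-4 stomatitis and no earlier grade 3-4 HFS meets both instructions, whether *toxicity* means stomatitis or either event. In the base case the choice is between 30 and 22.5 mg/m², assuming that cuts compound and that the patient had the one earlier reduction the table requires. The word *HFS* looks carried over from the HFS table. The grade 2 HFS row itself can be read without conflict, with *toxicity* meaning HFS, and is not claimed as an error. The consequence is inconsistent PLD dosing after a recurrence, with no effect on the design, the sample size or the primary analyses.

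**What to change.** In the same-dose branch of the grade 2 stomatitis row, replace *HFS* with *toxicity*, to match the grade 1 row. Add one line stating that *toxicity* in this table means stomatitis. Before the amendment is issued, check the row and that definition against the package insert the section cites, so that the meaning is settled in the protocol itself. With *toxicity* read the same way in both branches, each of the four histories falls in exactly one branch, which also closes the gap for patients with earlier HFS only. As an optional clean-up, write *HFS* in both branches of the grade 2 HFS row.

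The cost is one word, one definition line and a check against the insert. Design, sample size and analysis do not change.

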Pembrolizumab Event of Clinical Interest Guidance Document

Each of the events above is described within this guidance document, along with site requirements for reporting these events to the Sponsor. The information collected should be entered into the narrative field(s) of the Adverse Event module in the database (please note, if narrative entry into the database is not available, please use the narrative text box on the 1727/AER Form). If additional Medical History or Concomitant Medications are reported, the Medical History and Concomitant Medication modules in the database must be updated.

In addition, the guidelines include recommendations on the management of these ECIs. These guidelines are intended to be applied when the physician determines the events to be related to pembrolizumab. Note: if after the evaluation the event is determined not to be related, the physician is instructed to follow the ECI reporting guidance but does not need to follow the treatment guidance (below). Therefore, these recommendations should be seen as guidelines and the treating physician should exercise individual clinical judgment based on the patient. For any question of dose modification or other treatment options, the specific language in the protocol should be followed. Any questions pertaining to the collection of this information or management of ECIs should be directed to your local Sponsor contact.

Dose Modification/Discontinuation

The treatment guidance provides specific direction when to hold and/or discontinue pembrolizumab for each immune related adverse event. Of note, when the guidance states to “discontinue” pembrolizumab this is the permanent discontinuation of treatment with pembrolizumab. “Hold” means to stop treating with pembrolizumab but resumption of treatment may be considered assuming the patient meets the criteria for resumption of treatment.

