3.6 Neurologic

The following AE terms, regardless of grade, are considered ECIs and should be reported to the Sponsor within 24 hours of the event:

- Autoimmune neuropathy
- Demyelinating polyneuropathy
- Guillain-Barre syndrome
- Myasthenic syndrome

All attempts should be made to rule out other causes such as metastatic disease, other medications or infectious causes. However the AE should be reported regardless of etiology.

Course of Action

Grade 2 events:

- Report as ECI
- Moderate (Grade 2) – consider withholding pembrolizumab.
- Consider treatment with prednisone 1-2 mg/kg p.o. daily as appropriate
- Consider Neurology consultation. Consider biopsy for confirmation of diagnosis.
- Permanently discontinue for inability to reduce corticosteroid dose to 10 mg or less of prednisone or equivalent per day within 12 weeks.

Grade 3 and 4 events:

- Report as ECI
- Discontinue pembrolizumab
- Obtain neurology consultation. Consider biopsy for confirmation of diagnosis
- Treat with systemic corticosteroids at a dose of 1 to 2 mg/kg prednisone or equivalent once per day. If condition worsens consider IVIG or other immunosuppressive therapies as per local guidelines

When symptoms improve to Grade 1 or less, steroid taper should be started and continued over no less than 4 weeks.

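### For nine immune event terms with no row of their own, Table 3 governs pembrolizumab dosing but is less cautious than the protocol's Appendix B

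*Combined protocol and SAP*

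**What the plan says.** Section 6.2 states the governing rule: "Pembrolizumab must be withheld for drug-related toxicities and severe or life-threatening AEs as per Table 3 below". The title of Table 3 also points the reader to Appendix B.

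Table 3 has rows for diarrhea/colitis, liver tests, type 1 diabetes/hyperglycemia, hypophysitis, hyperthyroidism, hypothyroidism, infusion reaction, pneumonitis and renal events. Everything else goes to "All Other Drug-Related Toxicity". That row holds drug for a Grade 3 or severe event, allows restart at Grade 0-1, and stops permanently at Grade 4. It has no Grade 2 entry. Footnote 2 covers Grade 2: "Patients with intolerable or persistent Grade 2 drug-related AE may hold study medication at physician discretion". The Note under the table requires a permanent stop if a Grade 3 or severe event recurs, or if any event is life-threatening.

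Appendix B, section 1 (Overview), describes its own role in two ways. On holding and stopping it says: "The treatment guidance provides specific direction when to hold and/or discontinue pembrolizumab for each immune related adverse event". It also calls its recommendations guidelines and adds: "For any question of dose modification or other treatment options, the specific language in the protocol should be followed". When it says to discontinue, "this is the permanent discontinuation of treatment with pembrolizumab".

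**The concern.** An investigator who follows Table 3 exactly may re-challenge a patient who has recovered from a first Grade 3 Guillain-Barre or myasthenic syndrome, although the protocol's safety appendix directs a permanent stop. The same investigator may keep dosing through Grade 2 myocarditis, where the appendix directs a hold, in a patient who is also receiving PLD, itself listed as cardiotoxic in sections 2.2 and 7.1.1. Two sites could manage the same event differently and both comply. What is at stake is the safety of individual patients and consistency between sites, not the statistical conclusions.

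**Working it through.** The protocol states no figure on this point, so the main check is a side-by-side reading. Both texts concern events judged related to the drug, so their scope is the same.

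| Event with no Table 3 row | Grade | Table 3 (All Other row, footnote 2) | Appendix B | Differ? |
|---|---|---|---|---|
| Autoimmune neuropathy, demyelinating polyneuropathy, Guillain-Barre, myasthenic syndrome | 3, first event | Hold; may restart at Grade 0-1 | 3.6: "Discontinue pembrolizumab", meaning permanently | Yes |
| Same four terms | 2 | Optional hold | 3.6: consider withholding | No |
| Same four terms | 4 | Permanent stop | 3.6: permanent stop | No |
| Myocarditis, pericarditis, pancreatitis | 2 | Optional hold | 3.10: withhold | Yes |
| Same three terms | 1, not improving | No provision | 3.10: withhold | Yes |
| Same three terms | 3 | Hold; may restart | 3.10: hold; may restart | No |
| Adrenal insufficiency, hypopituitarism (symptomatic) | 2 | Optional hold | 3.3: hold | Yes |
| Same two terms | 3 | Hold | 3.3: hold | No |
| Rash, pruritus | 2-4 | Optional hold; hold; stop | 3.9: treat symptoms; hold; stop | No |

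**Count.** Neurologic at Grade 3: 4. Section 3.10 at Grade 2: 3. Section 3.3 at Grade 2: 2. Total 4 + 3 + 2 = 9.

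**Terms left out.**
- Ocular events: section 3.7 refers Grade 2 discontinuation back to the protocol.
- Thyroiditis and thyroid disorder: it is unclear which path in 3.3 they follow.
- The six hematologic diagnoses in 3.4: below Grade 3 they are events of clinical interest only if dose modification or systemic steroids are already required. The Grade 2 hold there does not reach every Grade 2 event.

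The two endocrine terms have a similar reporting threshold in 3.3, but they stay in. The 3.3 instructions for Grade 2-3 make reporting conditional while directing the hold without that condition; the 3.4 Grade 2 list opens with unconditional reporting. A reader who excluded them as well would be left with 4 + 3 = 7 terms.

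**Was the difference intended?**
- Where the protocol departs from Appendix B on Grade 2 infusion reactions despite premedication, it does so with event-specific text. Table 4 says refer to allergy; Appendix B 3.11 says stop permanently. No such text exists for the nine terms.
- Appendix B says so where it defers to the protocol (3.4 Grade 3, 3.7, restart after Grade 3 in 3.10). Section 3.6 has no such deferral.
- Appendix B gives hypophysitis and other symptomatic non-thyroid endocrine disorders one rule. Table 3 mandates the Grade 2 hold for hypophysitis only.
- Table 3 already stops permanently at Grade 3 for liver tests (with an exception), pneumonitis, renal events and infusion reactions.

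**Frequency.** Section 7.1.2 supports a rate for three of the nine terms: myasthenic syndrome, pancreatitis and adrenal insufficiency, read here as under 1% each at any grade. With n = 26, expected cases = 26p and the chance of at least one = 1 - (1 - p)^26.
- p = 1%: 26 x 0.01 = 0.26 cases; 1 - 0.99^26 = 23.0%.
- p = 0.1% (assumed low end): 26 x 0.001 = 0.026 cases; 1 - 0.999^26 = 2.6%.

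These are per-term figures. Only some grades are affected, so for those three terms the true figures lie below the 1% line. The documents give no rate for the other six, so no total across the nine can be formed.

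**The case against.** The strongest objection is that the documents settle precedence. A reader might infer that nothing says which text wins when an event has no row. The documents do not support that: Appendix B section 1 sends dose questions to the protocol, section 6.3.1 points to Section 6 for dose modification, and the All Other row is itself a protocol rule. This stands, and it fixes the form of the concern. There is no open contradiction; the text that governs is the weaker one. That does not remove the safety point.

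A second objection is that Section 6 is the study-specific rule and Appendix B generic guidance, so a difference alone proves no error. That is fair. But the infusion-reaction departure is written out for its event, and these differences arise only by default from a catch-all row.

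A third is that safeguards exist. Restart needs recovery to Grade 0-1; failure to recover, or to taper prednisone to 10 mg or less, within 12 weeks means discontinuation; recurrent Grade 3 and life-threatening events stop drug permanently; section 5.6 ends therapy for unacceptable events; and the neurologic and 3.10 terms must be reported within 24 hours at any grade. All true, and they limit the harm. None requires a stop after a first Grade 3 neurologic event that resolves in time, or a hold at Grade 2.

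**Conclusion.** The point holds for nine terms: four neurologic at Grade 3 (restart allowed against permanent stop) and five at Grade 2 (optional against directed hold). The neurologic difference is the main one. The count rests on the reading of 3.3 given in the working.

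Three stronger readings should be avoided. Table 3 does not require restart or continued dosing: holding or stopping satisfies both texts, while restarting or continuing satisfies only Table 3. Adding the six hematologic diagnoses, to reach 9 + 6 = 15 terms, is not supported because of their Grade 2 condition in 3.4. And nothing here touches alpha, power or endpoints.

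The probability is low: 0.026 to 0.26 expected cases per term if rates lie between 0.1% and 1%, a range that is an assumption for most terms. The consequence for an affected patient could be serious and the correction is cheap, so it is worth making.

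**What to change.** Add two rows to Table 3.

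- **Autoimmune neuropathy, demyelinating polyneuropathy, Guillain-Barre syndrome, myasthenic syndrome.** Grade 2: consider withholding. Grade 3-4: permanently discontinue.
- **Myocarditis, pericarditis, pancreatitis, and symptomatic endocrine disorders apart from hypo- and hyperthyroidism.** Grade 2-3: hold; for the first three, also hold at Grade 1 that fails to improve with symptomatic treatment. Restart under the table's existing Grade 0-1, 12-week and 10 mg prednisone rules. Grade 4: permanently discontinue. The separate hypophysitis and diabetes rows continue to apply to those events.

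Rows are better than a sentence saying that Appendix B applies where Table 3 has no specific row. Appendix B refers dose questions back to the protocol, so that sentence would be circular.

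The cost is a wording amendment with no new procedures or restart criteria, and slightly less pembrolizumab exposure in the few patients who have one of these events.
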